4.5 Clinical Experience

[figure not shown]
[figure not shown]
Antidepressant effects of high dose DCS were first noted in the late 1950's when it was first introduced as a treatment for tuberculosis (TB). Several clinicians noted dramatic improvement in patients' depressive symptoms, leading to suggestions of potential psychotropic effects. These effects were subsequently confirmed in small scale clinical studies. (Crane, 1959 and 1961). The mechanism of action was unknown at the time and the finding was not pursued. The interaction of DCS with the NMDA receptor was first demonstrated in 1989, (Hood et al., 1989), leading to some interest in NMDAR blockers as potential antidepressant treatments. (Trullas, Skolnick 1990; Skolnick et al., 1996). For example, both DCS and the related compound ACPC were shown to be active in mice, using the forced swim test for depression. (Lopes et al., 1997) To the best of our knowledge, no clinical antidepressant research programs targeting the NMDA receptor were initiated at that time.

Interest in the potential clinical use of DCS as an antidepressant agent was renewed following Berman's fortuitous observation of ketamine's rapid antidepressant effect in 2000. An initial study performed with DCS at a dose of 250 mg/d did not show therapeutic effect, but did demonstrate relative lack of psychotomimetic side effect when DCS was combined with concurrent antidepressant treatment (Heresco-Levy, Javitt et al., 2006). Based upon these safety data, a study using a higher dose of 1000 mg/d was initiated with results reported in 2013 (Heresco-Levy et al., 2013) (see Figure 1). At the higher, 1000 mg dose, significant beneficial effects were observed in 13 subjects vs placebo control with SSRI-nonresponsive depressive symptoms. The improvements were manifest within 2 weeks and persisted throughout the 6-week treatment period.

Figure 1 DCS vs. Placebo for Treatment of Depression

Source: [Kantrowitz, 2015](#)

The 2013 Heresco-Levy study provided initial evidence that DCS might be useful as an NMDAR- targeted antidepressant, but the time of onset for DCS alone was suboptimal for treating acutely depressed individuals. Therefore, an open-label study was performed in which subjects with bipolar depression received an infusion of ketamine on Day 1, followed by oral administration of DCS, titrated to a dose of 1000mg/day combined with lurasidone 66mg/day as individual commercially-supplied medications. Seven of 8 subjects completed the study and no adverse effects were noted. Over a period of 8 weeks, a > 75% reduction in suicidal ideation and a 50% reduction in depression was noted, using the Hamilton Depression Scale (HAM-D). (Figure 2; [Kantrowitz, 2015](#)). Note that suicidal ideation was eliminated entirely at 4 hours post-infusion of ketamine (Figure 3; [Kantrowitz, 2014](#)).

Figure 2 Depression Score after Ketamine followed by DCS + 5-HTZASource: [Kantrowitz, 2015](#)**Figure 3** Suicidal Ideation after Ketamine followed by DCS + 5-HTZASource: [Kantrowitz, 2014](#)

4.6 Investigational Therapy

The investigational therapy to be evaluated in this study consists of sequential treatment consisting of the following components:

1. an initial, one-time intravenous infusion of ketamine (0.5 mg/kg administered over 40 min) on Day 0, followed by
2. twice daily oral capsules of NRX 101 (d-cycloserine [DCS] + lurasidone), which is initiated on Day 1 (in subjects who respond to ketamine) and continued for up to 6 weeks. It is anticipated that subjects entering the study will be receiving concurrent disorder-directed treatment with various predefined combinations of medications. This treatment regime will be maintained upon entry into the study. However, any use of lurasidone, quetiapine, or olanzapine will be stopped at study entry. This regimen may be supplemented with mood stabilizers at the discretion of the treating physician.

Our clinical objective is to offer patients the clinical benefit of rapid reduction in symptoms of depression and suicidal ideation that has been observed with intravenous ketamine, while maintaining that benefit with a daily oral agent that does not have ketamine's potential for abuse and psychosis.

4.7 Dosing Rationale

The doses chosen for the three components of the sequential therapy are based on current dosing recommendations for each. In Stage 1, the one-time IV infusion of ketamine on Day 0 at 0.5 mg/kg over 40 minutes is below the lowest recommended IV concentration (1 mg/kg) to induce anesthesia, and is consistent with studies of ketamine for use in depression.

DCS is well-tolerated as a second-line treatment for TB at therapeutic split daily oral doses in the range of 500 to 1000 mg/day. The recommended oral dose of lurasidone for the treatment of acute depressive BD is 20 to 120 mg/day for up to 6 weeks. Therefore, dosing of the fixed-dose combination NRX 101 during Stage 2 will be twice daily over 6 weeks. The starting doses at 350 mg DCS and 16.5 mg lurasidone, and the titration over 5 days to a maximum of 950 mg DCS and 66 mg lurasidone are planned accordingly. Up-titration is built in to the dosing strategy in the case of subject agitation and a stepdown is allowed for somnolence.

For complete details regarding dosing recommendations, please see the product safety labeling for each of the drugs, which are included in the Investigator Brochure (IB).

5. OBJECTIVES

5.1 Primary Objective

The primary objective of the study is to test the hypothesis that following response to initial ketamine infusion, experimental drug NRX-101 (DCS + lurasidone) is superior to lurasidone alone and placebo as oral-therapy for delaying time to relapse (resulting in a new treatment plan or the subject relapsing to baseline levels of depression or suicidality) in subjects with documented bipolar depression presenting with symptoms of depression and suicidal ideation.

The primary study hypothesis (alternative hypothesis) is that ketamine and experimental drug NRX-101 (K/N) delays the time to documented relapse as compared to both lurasidone (L) and placebo (P) as measured by the hazard ratio (h) versus the null hypothesis of no delay in time to relapse for either comparator treatment (ketamine/lurasidone [K/L] and ketamine/placebo [K/P]) as follows:

$$H_0: h_{\text{NRX-101}} < h_L \text{ and } h_P$$

$$H_a: h_{\text{NRX-101}} \geq h_L \text{ and } h_P.$$

The primary outcome measure will be time to relapse, defined as the need to implement a new treatment plan or a return to baseline levels on the Columbia-Suicide Severity Rating Scale (C-SSRS), or the Montgomery Asberg Depression Rating Scale (MADRS) subset on the Bipolar Inventory of Symptom Severity (BISS).

All relapses will be documented by the site physician and reviewed on a monthly basis by a Relapse Adjudication Committee. The Relapse Adjudication Committee (RAC) will determine whether the relapse met the primary endpoint criteria.

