1. SYNOPSIS

Name of Investigational Product:	NRX-101 (administered to subjects who respond to an intravenous infusion of ketamine - 0.5 mg/kg administered over 40 min; on Day 0)
Name of Active Ingredient:	Fixed dose combination of d-cycloserine + lurasidone
Reference Product(s):	Lurasidone/placebo
Title of Study:	NRX-101 for the Treatment of Acute Suicidal Ideation and Behavior (ASIB) in Bipolar Depression
Phase of Development:	Phase 2b/3
Study Site(s):	Approximately 12 study sites which may be either inpatient psychiatric hospitals or community mental health centers/bipolar clinics with immediate access to inpatient care facilities. All sites will have a minimum of 12 months prior experience in the use of ketamine for stabilization of patients with ASIB in Bipolar Depression as part of their practice of medicine.
Study Duration:	Screening: up to 48 hours; IV ketamine Day 0; 6-week treatment; 4 week follow up
Background and Rationale:	DCS and Lurasidone, taken together, have been shown to maintain a 50% reduction in depression and a 75% reduction in suicidality following a single infusion of ketamine in patients with suicidal ideation and bipolar depression. Ketamine is increasingly used in medical practice to achieve rapid stabilization of patients with ASIB. However, the duration of ketamine effect is limited and its repeated use for maintenance of stabilization is not proven.
Objectives:	
The objectives of the study are as follows:
 
Primary Objective:
 
 The primary objective of the study is to test the hypothesis that following stabilization of depression and ASIB in response to initial ketamine infusion, NRX-101 is superior to lurasidone alone and also superior to placebo as oral-therapy for delaying time to relapse (resulting in a new treatment plan or the subject relapsing to baseline levels of depression or suicidality) in subjects with documented bipolar depression presenting with symptoms of depression and suicidal ideation. 
Secondary Objectives:
 
 To demonstrate superiority over placebo and over lurasidone alone in maintaining remission from depression in bipolar disorder. To demonstrate efficacy can be sustained with NRX-101 dosing regimens To demonstrate NRX-101 safety

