13.4 Hypothesis Tests

13.4.1 Primary Hypotheses

The primary study hypothesis (alternative hypothesis) is that Ketamine and experimental drug NRX-101 (K/N) delays the time to documented relapse as compared to both lurasidone (L) and placebo (P) as measured by the hazard ratio (h) versus the null hypothesis of no delay in time to relapse for either comparator treatment (Ketamine/lurasidone [K/L] and Ketamine/placebo [K/P]) as follows:

- H₀: $h_{\text{NRX-101}} < h_L$ and h_P
- H_a: $h_{\text{NRX-101}} > h_L$ and h_P

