13.8 Sample Size Calculations

13.8.1 Allocation

To encourage study participation, a 2:1:1 randomization will be used where at most half as many subjects will be assigned to the lurasidone and placebo arms as compared to the K/N study arm. The goal will be to have 62 subjects randomized to K/N and 31 subjects randomized to each of K/L and K/P for a total of 124 randomized subjects. The randomization takes place among Ketamine responders once confirmed by Medical Monitor.

13.8.2 Stage 1

The study goal is to achieve a total of 124 Ketamine responders for the Stage 2 evaluation. A total of 192 subjects are projected to be enrolled but this number may be reached sooner if the cumulative effect of the Ketamine response rate exceeding 70%, if the Stage 1 loss rate being less than 8% (15 subjects), or if the Stage 2 loss rate being less than 8% (9 subjects). Thus, there would be 177 subjects who complete Stage 1 before considering Ketamine response. The literature and prior experience suggests that 70% of those treated with ketamine will have an adequate reduction in depression and suicidality which equates to 124 Ketamine responders (177×0.7) who would be available for randomization. More subjects will need to be enrolled if the Ketamine response rate was lower than 70% or the randomization refusal rate was higher than 8%, considered to be part of Stage 2 losses.

13.8.3 Stage 2

Stage 2 will investigate the study hypotheses. The primary efficacy hypothesis is that K/N will delay the time to relapse relative to K/L and K/P. The goal will be to have 62 subjects randomized to K/N and 31 subjects randomized to K/L and K/P. These numbers are based on the Ketamine Responders. See **Error! Reference source not found.** for the total number of K/N and K/L subjects required to test the primary efficacy hypothesis. The sample size requirements are shown just for K/N and K/L. .

The study is powered based on the number of subjects randomized to K/N vs. K/L. In order to achieve 90% study power with two-sided 0.05 Type I error, a total of 56 K/N subjects, 28 K/L subjects, and 28 K/P subjects must be evaluated for time to relapse over the full 6 weeks. This is based on the assumption of a 30% relapse rate in the K/N treatment group and a 70% relapse rate in the K/L and K/P treatment groups. A larger gap in the relapse rate is expected based on the literature, so this is believed to be a conservative assumption. These calculations assume a loss of 8% during Stage 2.

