13.9 Overall Type 1 Error Control

The overall Type I error is two-sided 5%. No interim analyses are planned.

A hierarchical testing plan is in place to control Type I error to extend labeling claims in the following pre-defined testing order where statistical significance (two-sided $p < 0.05$) is required at each step:

1. Primary: K/N will delay time to relapse relative to K/L and K/P
2. Secondary: K/N will separate from K/L and K/P by 72 hours, with sustained difference between groups thereafter

3. Secondary: All-cause discontinuation (including discontinuation for continued suicidal ideation) will be lower in K/N than K/L and K/P.
4. Secondary: K/N will separate from K/L and K/P starting at Day 7, with sustained difference thereafter
5. Secondary: Improvements within the K/N group observed at Week 2 will remain stable to end of study.

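### The printed primary hypotheses in 5.1 and 13.4.1 run opposite to the prose and leave a win over one comparator undefined, and 13.9 does not say that both pairwise tests must succeed

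*Combined protocol and SAP*

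**What the plan says.** The aim is stated in words in several places. The Synopsis tests whether "NRX-101 is superior to lurasidone alone and also superior to placebo as oral-therapy for delaying time to relapse". Sections 5.1, 6.1 and 13.4.1 also speak of both comparators, and 5.1 and 13.4.1 set the alternative against a null worded as "versus the null hypothesis of no delay in time to relapse for either comparator treatment".

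The formal lines in 5.1 then read "H_0: h_{\text{NRX-101}} < h_L \text{ and } h_P" and "H_a: h_{\text{NRX-101}} \geq h_L \text{ and } h_P". Section 13.4.1 prints the same direction, with a strict inequality in Ha.

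The first step of the testing hierarchy in 13.9 is "Primary: K/N will delay time to relapse relative to K/L and K/P". Two-sided p<0.05 is required at each step, but 13.9 does not say how the two pairwise results combine into one pass or fail. Sections 13.10.4 and 13.10.5 name a proportional hazards model with study treatment as a covariate as the primary analysis, and do not name the pairwise contrasts.

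On size, 13.8.3 states: "In order to achieve 90% study power with two-sided 0.05 Type I error, a total of 56 K/N subjects, 28 K/L subjects", with 28 K/P subjects as well. It assumes a "30% relapse rate in the K/N treatment group and a 70% relapse rate in the K/L and K/P treatment groups" and bases power on K/N versus K/L alone.

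**The concern.** A treatment that delays relapse has the lower hazard. The printed H0 is therefore the region of benefit, and the printed Ha is the region of no benefit or worse. That contradicts the sentence directly above it.

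The pair also leaves a gap. If NRX-101 has a lower hazard than one comparator but not the other, neither hypothesis is true. That is a realistic result in a three-arm trial with an active control. For a claim against both comparators, the null has to be that NRX-101 fails to beat at least one of them. The verbal null does not settle this, because no delay for either comparator can mean no delay against at least one or no delay against both.

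The practical stake is step 1 of 13.9, which opens the way to every secondary labelling claim. With no written pass rule, a win over placebo alone has no defined status. Yet K/N versus K/L is the comparison that isolates what d-cycloserine adds.

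**Working it through.** **Inputs.** 56/28/28 evaluable in K/N, K/L and K/P; relapse at 6 weeks 30/70/70%; two-sided 0.05; 90% power (all from 13.8.3). Hazard ratio formula h = ln(p1)/ln(p2) for relapse-free proportions (Table 12).

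**The plan's own figures.**
- ln(0.30)/ln(0.70) = 3.376, as in Table 12 (control over NRX-101).
- Freedman's formula (equal allocation) for 90% power: (1.960 + 1.282)² × (4.376/2.376)² = 35.6, so 36 events.
- Expected events in 56 + 28: 56 × 0.30 + 28 × 0.70 = 16.8 + 19.6 = 36.4. The pairwise 90% reproduces. Schoenfeld's formula at 2:1 needs 32 events and gives 93.3% power at 36.4.

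**Direction.** Under exponential times, the hazard per 6 weeks is −ln(0.70) = 0.357 on K/N and −ln(0.30) = 1.204 on each comparator. The ratio is 0.357/1.204 = 0.296, so the effect the trial is sized to detect lies inside the printed H0.

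**Completeness.**

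| True state of h(NRX-101) | As printed in 5.1 | For a both-comparators claim |
|---|---|---|
| Below both | H0 | Ha |
| Below L, not below P | neither | H0 |
| Below P, not below L | neither | H0 |
| At or above both | Ha | H0 |

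**What the pass rule changes.** Only wins favouring K/N count, so each pairwise test has a 2.5% false-win rate.
- All arms equal: the two tests share the K/N arm, with correlation (1/56)/(1/56 + 1/28) = 1/3. The bivariate normal gives P(both) = 0.0027 and P(either) = 2 × 0.025 − 0.0027 = 0.0473. Log-rank simulation (8,000 trials, 70% relapse in each arm) gives 0.3% and 5.1%.
- NRX-101 equal to lurasidone (30% relapse each), placebo 70%: log-rank simulation (8,000 trials) passes step 1 in about 96% if either win suffices and about 3% if both are required.

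**Power to win both at 30/70/70.**
- Unpooled variance: 1/16.8 + 1/19.6 = 0.1105, SE 0.3325. ln(3.376)/0.3325 = 3.66. Power is 95.5% per comparison; with correlation 0.0595/0.1105 = 0.54, power for both is 92.2%.
- Schoenfeld: √(36.4 × 2/9) × ln(3.376) = 3.46. Power is 93.3% per comparison; with correlation 1/3, power for both is 87.9%.
- Log-rank simulation (4,000 trials): about 96% per comparison and 92.5% for both.

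**The case against.** The case for leaving this alone is that the intent is plain. The Synopsis, 5.1, 6.1, 13.4.1 and 13.9 all describe delay against lurasidone and placebo, several of them with the word both. Nothing in the documents proposes a claim on one comparator. Sample size, alpha, endpoint and model would all stay as they are. Much of this stands. It makes the correction one of wording, and it rules out four stronger readings.

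- A reader might infer that rejecting the printed H0 would be taken as evidence of harm. The documents do not support that. The analysis is a two-sided comparison in a proportional hazards model, its direction is read from the estimate, and the direction of success is stated in words throughout.
- A reader might put the false-claim rate at 2 × 5% = 10% if either comparison sufficed. That counts wins for the comparator. Counting wins for K/N, the bound with all arms equal is 2 × 2.5% = 5%.
- A reader might say the both-comparators aim is missing. It is present in prose; what is missing is a matching formal null and a stated pass rule.
- A reader might fault every and in the two lines. In a correctly directed Ha, and is right; only H0 needs or.

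One could also try to rescue the inequalities by reading h as Table 12's control-over-NRX ratio, where larger is better. That fails, because h carries a separate subscript for each arm, so it is an arm's hazard and not a ratio. A text-reading fault is unlikely, since the reversed direction appears in two sections. The ≥ versus > difference between them could be one, and nothing here rests on it.

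What the objection does not answer is that 13.9 requires significance at step 1 without saying of which test or tests.

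**Conclusion.** The point holds as a correction to the formal primary hypotheses and the decision rule. In both sections the printed inequalities contradict the prose, the two hypotheses do not cover all outcomes, and the condition for passing step 1 is unstated. The consequence is modest when all arms are equal (about 5% against 0.3%). It is large where NRX-101 adds nothing to lurasidone but both beat placebo (about 96% against 3%).

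The power figures assume exponential relapse times, complete 6-week follow-up of 56/28/28, the 30/70/70% relapse rates, and log-rank tests standing in for the covariate-adjusted model. Power for both depends on those rates. At the 52% versus 30% relapse-free case also shown in Table 12, it is only about 30–36%, with about 50–55% per comparison. The statement that no larger sample is needed is therefore made at the rates in 13.8.3.

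**What to change.** In 5.1 and 13.4.1, replace the formal lines with:

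- H0: h(NRX-101) ≥ h(L) or h(NRX-101) ≥ h(P)
- Ha: h(NRX-101) < h(L) and h(NRX-101) < h(P)

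In 13.9, add that step 1 is passed only if K/N versus K/L and K/N versus K/P each have two-sided p<0.05 favouring K/N.

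The cost is wording only. Because both tests must succeed, each can be run at the full two-sided 0.05 with no alpha split, and the 112 evaluable and 124 randomised subjects stand. The change should be made before unblinding, because a pass rule chosen after the results are known would not be credible.

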5.2 Secondary Objective

The secondary objectives of the study are the following:

- To demonstrate bipolar depression efficacy
- To demonstrate efficacy can be sustained with NRX-101 dosing regimens
- To demonstrate NRX-101 safety

The secondary study hypotheses (alternative hypotheses favoring K/N vs. K/L and K/P) are the following:

1. K/N will favorably separate from both K/L and K/P by 72 hours, with sustained difference between groups thereafter.
2. All cause discontinuation (including discontinuation for continued suicidal ideation) will be lower for K/N than both K/L and K/P.
3. K/N will favorably separate from K/L and K/P starting at day 7, with sustained difference thereafter.
4. Improvements within the K/N group observed at Week 2 will remain stable to end of study.

-
5. C-SSRS scores will remain <4 for 4 weeks following treatment discontinuation (i.e., “crisis” will resolve within the 6 week time period with more favorable outcomes in the K/N group as compared to K/L and K/P).

Additionally, symptom improvement will be evaluated by assessing changes in the secondary outcome measures: C-SSRS, CHRT, and the BISS (including its subscales). These measures will be assessed at the times specified on the Study Activity Schedule, Table 3.

6. STUDY DESIGN

6.1 Overview

The multi-center study will consist of a 6-week, parallel group, double-blind, randomized, adaptive, superiority trial designed to test the hypothesis that following response to ketamine infusion, experimental drug NRX-101 (DCS + lurasidone) is superior to both lurasidone alone and placebo as oral-therapy for delaying time to relapse (resulting in a new treatment plan or the subject relapsing to baseline levels of depression or suicidality) in subjects with documented bipolar depression presenting with symptoms of depression and suicidal ideation.

6.2 Methods

[figure not shown]
In Stage 1 eligible subjects will initially receive an infusion of open-label ketamine 0.5mg/Kg. Those who do not respond to ketamine infusion as measured by a $\geq 25\%$ improvement in the MADRS subset on the BISS and a reduction in C-SSRS suicidal ideation to ≤ 3 at 24 hours post infusion will be withdrawn from the study and treated according to standard of care for subjects with suicidal ideation or behaviors.

Subjects who respond successfully to ketamine infusion, as defined above ($\geq 25\%$ improvement in the MADRS subset of the BISS and C-SSRS ≤ 3) at 24 hours post infusion will proceed to Stage 2 and be randomized to either experimental drug NRX-101 (DCS + lurasidone), lurasidone alone, or placebo. Efficacy data will be collected for the subjects responding to ketamine through 6 weeks or until earlier rescue.

Subjects may be terminated from the study and rescued with alternative therapy at any time if, in the opinion of the investigator, subjects have a significant safety risk for clinical deterioration or suicide.

